1. Counseling twice weekly on diet and nutrition will improve food choices to more healthy choices of fresh fruits and vegetables and low fat protein sources. To test this hypothesis, patients will undergo a food frequency questionnaire at baseline to document choices prior to intervention. A food frequency questionnaire will be performed at the end of the intervention to determine the effect of counseling on protein source, number of calories, and frequency of fresh fruits and vegetables. Counseling will consist of the diabetes prevention program counseling which is a well-established, well-verified intervention, commonly accepted as an effective means of providing a standardized nutritional education.

2. The combination of exercise and dietary intervention positively affects body composition. With this hypothesis we will test whether muscle strength (Biodex measurements) and muscle mass (DEXA scan) changes after 12 months of an exercise intervention. We hypothesize that the transplant itself will not affect activity levels, strength levels or muscle mass. Baseline measurement will be performed before the intervention, at 6 months post intervention, and the final measurement would be taken at 12 months with muscle mass measured by DEXA and strength measured again by Biodex.

3. Patients receiving strength training will have significantly higher activity levels when compared with no intervention or physical therapy. The rationale for this hypothesis is that patients without strength training will fail to increase muscle mass and strength and this inability will translate to persistently lower activity levels than those patients with strength training. Once again levels will be documented with an accelerometer and PROMIS questionnaires, 6 months and 12months to document the effect of intervention. In addition, if patients in the control group and GH group decide to

have the optional muscle biopsy, it will help evaluate how targeted exercise may change muscle development measuring expression of mature microRNAs using total RNA extraction.

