4. Patients with strength training will activate type II macrophages which are anti-inflammatory and pro-regenerative, tipping the balance away from inflammation towards regeneration when compared to the other treatment groups. Since strength training is likely to initiate signals of muscle regeneration, and since type II macrophages play a key role in this effect, it is possible that increasing the signaling to the muscle for regeneration may also increase the proportion of active type II macrophages which are anti-inflammatory. To test this hypothesis, we will test the proportion of peripheral blood M1/M2 macrophages at baseline, 6 months and 12 months after the initiation of the intervention. Recognizing that immunosuppression may significantly confound this proportion and overall suppress it, we will also test circulating levels of pro-inflammatory cytokines such as C-reactive protein(CRP), IL-6, IL-1, TNF-alpha, homocysteine, adiponectin, leptin, and resistin as well as pro-regenerative cytokines such as TGF-beta and IL-10.

5. We expect patients with strength training will experience less renal dysfunction, decreased hemoglobin A1C, increased peripheral vascular function, decreased fasting blood sugar when compared to the other treatment groups. The rationale for this hypothesis is the finding that muscle mass provides active regulation of glucose and other metabolites. Therefore increasing this may provide improved metabolic function. These laboratory panels are part of the standard transplant follow-up labs and add no cost to the project.

6. Patients with strength training will have an overall improved sense of well-being and energy level compared to those with physical therapy or no treatment. With twice weekly counseling for activity and nutrition, patients will be asked about their general health, mental health and pain intensity using the PROMIS questionnaires.

METHODS

Setting: The study will include 225 patients, to achieve a goal of 180 patients in the GH study group and 45 patients in the control group. Every patient will be followed for 3 years after the start of the intervention. Patients will start the intervention at least 2 months post-transplant; however they can be enrolled prior to transplant.

Main Study Inclusion criteria:

- Successful kidney transplantation (KTx) with primary graft function
- Age between 18 and 65 years

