- Adequate cognitive ability to complete the questionnaires, give consent for the study and follow the physical and diet instructions

Main Study Exclusion criteria:

- transplant of any other organ besides kidney alone or a combination of a kidney/pancreas

- non-ambulatory or significant orthopedic problems
- cardiac/pulmonary disease that contraindicate the physical training
- any contraindication to exercise testing per the American Heart Association
- unable to comply with the training program

Muscle Biopsy Inclusion:

- Age between 18 and 65 years
- Patients who have a brachial–cephalic arteriovenous fistula (AVF) in the elbow or brachial–basilic AVF in the arm
- Exercise Arm- the biopsy will only be performed once, after the 12 month exercise intervention is completed (which will be longer than 1 year post transplant surgery)
- Control Arm- this procedure will be performed once, around one year post transplant surgery (may occur at any time during the study)

Muscle Biopsy Exclusion:

- Patients that do not meet the inclusion criteria

Identifying potential subjects for recruitment:

A waiver for an alteration of consent and waiver of documentation of consent is being requested for review of medical records to identify potential patients for study recruitment and also for a telephone screening process for patients that response to a recruitment flyer. The principal investigator already has access to these records as part of daily care for all patients seen in clinic. This presents no more than minimal risk since this data will be kept confidential.

Moreover, as part of the telephone screening process for patients interested in this study there will be oral consent obtained to start the screening process in order to determine if the patients are eligible to be in the study. If the patients are eligible, they will be schedule for a visit where they will be consented to be in the study.

Randomization: All patients who meet the enrollment criteria will be randomized 4:1 to the GH group or the control group.

- GH group: patients will be treated for 12 months with the GH method (Appendix 1) for one hour twice a week

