- Control group: patient will be treated according to the standard of care for post-transplant recipients; control patients will be offered the opportunity to undergo the GH regimen for the 1 year after their final visit as a control patient. If the control patients chose to undergo the GH regimen, the extended follow up will be completed after 1 year from their final GH visit (totaling 4 years from the start of intervention).

Long-term follow-up

After the 12 month intervention period all patients will be followed for 2 additional years. Patients will be contacted by phone to assess current activity level, employment status, graft function and current weight. Patient's medical records will also be reviewed to confirm BMI and graft function. This will be done every 6 months.

A separate waiver of documentation of consent, for long-term follow up, is being requested for patients that have previously enrolled and completed the study (January 3, 2012 to July 28, 2014).

Parameters to analyze in all patients:

The PROMIS v.1.1 - Global Health short form will be administered to all patients at the time of enrollment, 6 months and at the end of the study (12 months). The PROMIS v.1.1 - Global Health short form will assesses health in general (i.e. overall health). The PROMIS Global Health short form is a 10-item instrument representing multiple domains (physical function, fatigue, pain, emotional distress, social health) as well as perceptions of general health that cut across domains. Global items allow respondents to weigh together different aspects of health to arrive at a “bottom-line” indicator of their health. Similar global health items have been found predictive of future health care utilization and mortality.

PROMIS 29 Profile v2.0 will be administered to all patients at the time of enrollment, 6 months and at the end of the study (12 months). The PROMIS 29 Prolife v2.0 is a short form containing four items from seven PROMIS domains (Depression, Anxiety, Physical Function, Pain Interference, Fatigue, Sleep Disturbance, and Ability to Participate in Social Roles and Activities) along with a single item on Pain Intensity.

Multiple studies have been conducted by the PROMIS Network validating these instruments. Studies are shown at: <http://www.nihpromis.org/science/validitystudies.aspx>

Body composition and strength

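### Hypotheses 3 and 6 and the Benefits text name a physical therapy comparator or arm that is not randomised, and the stated between-group tests omit strength, accelerometer activity, vascular function and food frequency

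*Combined protocol and SAP*

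**What the plan says.** **Arms.** The Randomization paragraph states: "All patients who meet the enrollment criteria will be randomized 4:1 to the GH group or the control group". The Setting paragraph sizes them "to achieve a goal of 180 patients in the GH study group and 45 patients in the control group". For the control group, the "patient will be treated according to the standard of care for post-transplant recipients". The Statistical analyses section compares two groups.

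**Comparators in the hypotheses.** Hypothesis 3: "Patients receiving strength training will have significantly higher activity levels when compared with no intervention or physical therapy". Hypothesis 6 predicts better well-being and energy "compared to those with physical therapy or no treatment". Hypothesis 4 predicts an effect "tipping the balance away from inflammation towards regeneration when compared to the other treatment groups", and Hypothesis 5 ends "decreased fasting blood sugar when compared to the other treatment groups". The Benefits paragraph in section 6 credits patients in a supervised physical therapy arm, alongside the GH arm, with extra supervision.

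**Outcomes and tests.** The Statistical analyses section lists five efficacy parameters: perceived well-being, lean/fat ratio, BMI, inflammatory parameters and metabolic parameters. The sentence naming the tests applies them to that list. Hypothesis 5 also includes vascular function: "We expect patients with strength training will experience less renal dysfunction, decreased hemoglobin A1C, increased peripheral vascular function". Hypothesis 2 asks whether Biodex strength and DEXA muscle mass change after 12 months. Hypothesis 1 uses a food frequency questionnaire before and after the intervention.

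**The concern.** There are two gaps between what the hypotheses promise and what the design and analysis deliver.

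The first is a comparator with no patients. A reader of Hypotheses 3 and 6 would expect evidence that GH beats physical therapy, and the trial cannot supply it.

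The second is that outcomes named in four hypotheses fall outside the only stated between-group tests. For activity and vascular function, a contrast is claimed with no summary measure or test attached, so the measure could be chosen after the data are seen. For food frequency and Biodex strength, the wording is before/after. Change within GH patients mixes the programme with anything that moves both arms, such as recovery after transplant or the nutrition education that the Counseling paragraph gives to everyone. For strength, a randomised comparison that removes this shared change is already available and would go unused.

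**Working it through.** **1. Do the two arms use up the sample?** Inputs are from the Setting and Randomization paragraphs. 180 + 45 = 225, and 180 / 45 = 4.0. The stated total and the 4:1 ratio are reproduced. Patients left for a third arm: 225 − 180 − 45 = 0.

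**2. Hypotheses set against arms and tests.**

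| Hypothesis | Comparator as worded | Reached by the five parameters | Not reached |
|---|---|---|---|
| 1 | none (before/after) | – | food frequency |
| 2 | none (before/after) | DEXA part, through the lean/fat ratio | Biodex strength |
| 3 | no intervention, or physical therapy | possibly PROMIS, through well-being | accelerometer activity |
| 4 | plural groups | inflammatory parameters | – |
| 5 | plural groups | glucose, HbA1c | vascular function |
| 6 | physical therapy, or no treatment | well-being | – |

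Vascular function is hard to read into the metabolic item, because the Methods give it a heading separate from metabolism and renal function. Renal function is unclear: creatinine sits under the joint metabolism and renal heading, while the efficacy list says only metabolic.

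**3. Are the omitted outcomes measured in both arms?** Biodex, accelerometer and vascular tests fall under the Methods heading for parameters to be analysed in all patients, and the schedule table has them at baseline, 6 and 12 months. Food frequency appears only in Hypothesis 1. It is in neither the all-patients list nor the GH-only list, and the schedule says only questionnaires. The Food Journal is no substitute: it is GH-only, and the protocol says it is not a measurement given at a set time.

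**4. How much choice is open?** Biodex gives knee extensor and flexor values on both sides, 2 × 2 = 4 candidates. No accelerometer summary is defined. The Methods name about eight vascular tests, some overlapping (pulse wave velocity already covers sites that return under wrist and central stiffness), and Hypothesis 5 concerns only peripheral function.

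**5. Would added tests matter?** The inflammatory item covers 8 pro-inflammatory markers, 2 pro-regenerative markers and the M1/M2 proportion, which makes 11. The metabolic item covers glucose, HbA1c and four lipids, which makes 6 without creatinine. With one test each for well-being, lean/fat ratio and BMI, the count is 11 + 6 + 3 = 20. At 0.05 each and assuming independence, the chance of at least one false positive is 1 − 0.95^20 = 0.64. With three more tests it is 1 − 0.95^23 = 0.69.

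**6. Precision of the reported differences.** The 95% half-width in SD units is t × √(1/n₁ + 1/n₂).
- 180 v 45: SE = √(1/180 + 1/45) = 0.1667; × 1.971 = 0.33 SD.
- 144 v 36 (20% dropout, an illustrative assumption, since the documents give none): SE = 0.1863; × 1.973 = 0.37 SD.

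**The case against.** The best defence is that the physical therapy wording is leftover text. The aim, sample size, randomisation and statistics are all two-arm, so nobody following the plan would run a wrong test. That stands: the five listed comparisons are unaffected. It does not excuse current text that states an untestable contrast and tells readers of the Benefits paragraph about an arm that is not there.

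A second defence is that a short list of formal tests is a legitimate choice, and that the Methods heading already signals analysis of every measure in all patients. This also stands in part, and it is why the fix asks for estimates and not for more tests. But a heading names no contrast, summary measure or time point.

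Three stronger readings are tempting and are not supported.
- A reader might infer that four of six hypotheses name a missing arm. Only 3 and 6 name physical therapy; 4 and 5 merely use a plural. In 3 and 6, the no-intervention and no-treatment wording can be read as the control arm.
- A reader might infer that none of the four outcomes has a stated GH-versus-control comparison. Hypotheses 3 and 5 do state a contrast, for activity and vascular function; what they lack is a test.
- A reader might infer that comparing GH with control would show the effect of counselling. GH combines exercise, psychology and nutrition, so the contrast speaks only to the whole programme.

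**Conclusion.** The point holds as a mismatch between hypotheses, design and tests. The physical therapy comparator has 0 of 225 randomised patients. Four hypothesised outcomes are outside the five tested parameters: two (activity, vascular function) have a contrast without a test, and two (Biodex strength, food frequency) are framed as before/after change. Three of the four are already scheduled at three time points in all patients; the arm coverage of food frequency is unstated.

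This should be corrected, but it does not invalidate the listed comparisons. The documents also do not show that a physical therapy arm was ever opened or that data from one exist. The arm and outcome findings rest on the text alone. The figure of about 20 tests assumes one test per named marker and one each for the other three items; the 64% and 69% figures further assume independence.

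**What to change.** - Remove the physical therapy comparator from Hypotheses 3 and 6 and the physical therapy arm from Benefits. State Hypotheses 3 to 6 as GH versus standard-of-care control.
- Restate the strength part of Hypothesis 2 as the GH-versus-control difference in 12-month change, on one pre-named Biodex measure.
- Report one pre-named accelerometer summary and one pre-named peripheral vascular measure in the same way.
- Label all three as supportive additions, date them, and give 95% confidence intervals with no significance claim. The claim of significance in Hypothesis 3 should be reworded to match.
- Restate Hypothesis 1 as GH versus control only if food frequency was collected in both arms; otherwise report it as descriptive.
- Credit any difference to the GH programme as a whole, not to counselling alone.
- State whether creatinine belongs to the metabolic item.

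The cost is protocol and SAP wording, with no new visits for the three scheduled outcomes. The claims become narrower. The additions are late, since the Long-term follow-up section refers to patients who completed the study between 2012 and 2014, so their date must be visible. Food frequency in controls may not be recoverable. Reporting intervals only adds no test to a plan that already implies about 20 uncorrected ones.

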Typically, fitness programs are not customized to fit with a patients' physical and emotional life resulting in a much more limited health impact, shorter term participation, unsustainable changes, and an eventual return to the patients' status quo at the beginning of the program. However, the effective interplay of the distinct disciplines of fitness, psychology and nutrition is critical to the GH Method's success in achieving significant and sustainable health improvements in our patients measured in improved bodily function, mental health, and quality of life.

- 2) Build and expand their life tissue.

The physical exercise component of the GH Method focuses on using the least amount of a patients' energy to achieve the maximum health improvements. We believe the most effective strategy for maximizing patient improvements with minimal energy is to focus on the building and expansion of patients' life tissue or muscle mass. This focus on the development of life tissue with minimal energy expenditure informs the strategy, intensity, techniques, and process of the physical exercise of the GH Method.

Many exercise programs focus on improving many aspects of patients' physical health, while the GH Method focuses on strategies designed to maximize the development of life tissue. This systematic strategic focus on muscle mass development informs every aspect of the GH Method and is a critical driver of the significant measurable improvements experienced by patients.

3) Help them change their feelings and thinking patterns

The GH Method is designed to engage patients in an ongoing re-evaluation of their own health and behaviors, resulting in increased self-awareness of the cause-effect relationship of their lifestyle choices on their overall health and well being. While we use a range of strategies including cognitive behavior techniques, our more novel approach is to focus first on changing how patients physically feel and then engaging in cognitive therapy techniques to help them change their thinking and behaving patterns leveraging their already more positive feelings. We believe the most effective way to help patients modify behaviors is focus on helping them achieve a paradigm shift in their feelings from passive and negative regarding their health towards more positive and empowered feelings about their health before embarking on more detailed thinking and behaving pattern changes.

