reporting done via the Lifestyle Inventory, understand their eating and sleeping patterns in greater detail by eliminating their opinions and emotional relationship and just focusing on actual intake, and provide a tool for ongoing monitoring and an opportunity for increasing patient's self-reflection on their food and sleeping habits. This will only be administered to the GH patients. Importantly, this is not a measurement tool that we would give at a specific time during the study; it is being used during the study by the research personnel and GH Method personnel to help manage self-reported behavior changes with the patients.

Counseling

Patients in the both arms will be counseled regarding weight loss per standard of care which consists of a pre-transplant and a post-transplant nutrition evaluation and education.

Video recording (optional)

Video recordings will be an option on the consent form for patients that are randomized into the GH exercise group. The option to be video recorded by the GH team at the beginning and end of the patient's 12 months of training. The recordings will be used to compare the progress of the patient from the beginning and end of GH training.

GH Study Visits:

At least one week prior to the first GH session with a patient, the written assessments will be completed and returned to GH personnel for scoring and processing. The first four GH sessions (over 2 weeks) for any patient will be 75 minutes. Following the first 4 sessions, ongoing patients will be slotted into recurring 60 minute time slots for the remaining 50 weeks. All of these visits will occur in the UIC Disability Health and Social Policy Building (DHSP) located at [name] in Suites 158, 190, and 195. The procedure visits at baseline, 6 and 12 months will take 2-3 hours.

At least twice per week, GH personnel will attempt to follow-up with patients via text message, email or a phone call to evaluate their physical recuperation and overall health and energy or to track their performance with a behavior change goal.

Patients will be asked to complete a physical regimen based on the following:

Summary of GH Study Visits:

- Patients may be asked to repeat previous weeks and/or skip a particular week depending on their energy, progress, and overall health.

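### Hypotheses 3 to 6 credit strength training, but the two-arm design can only show the effect of the whole GH programme against standard care

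*Combined protocol and SAP*

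**What the plan says.** Under Hypotheses, four of the six items name strength training as the treatment:

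- Hypothesis 3: "Patients receiving strength training will have significantly higher activity levels when compared with no intervention or physical therapy". The rationale is that patients without it will not gain muscle and so stay less active.
- Hypothesis 4: "Patients with strength training will activate type II macrophages". The rationale is that strength training signals muscle regeneration, in which these cells take part.
- Hypothesis 5: "We expect patients with strength training will experience less renal dysfunction, decreased hemoglobin A1C", together with better vascular function and fasting glucose. The rationale is the metabolic role of muscle mass.
- Hypothesis 6: "Patients with strength training will have an overall improved sense of well-being and energy level compared to those with physical therapy or no treatment". Its next sentence mentions twice-weekly counselling on activity and nutrition.

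Hypothesis 2 is worded differently: "The combination of exercise and dietary intervention positively affects body composition". The aim at the end of Background also refers to a joint activity and nutrition programme compared with standard care.

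Randomization creates two arms, GH and control, in a 4:1 ratio (180 and 45). Controls receive standard care. The GH Method and Philosophy section says that "the effective interplay of the distinct disciplines of fitness, psychology and nutrition is critical" to the method's success.

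Under GH Study Visits, the GH arm has two sessions a week for a year, and "At least twice per week, GH personnel will attempt to follow-up with patients". Under Counseling, both arms receive the standard nutrition evaluation and education before and after transplant.

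**The concern.** The treatment named in Hypotheses 3 to 6 is one ingredient of what is randomised. The documents themselves supply rival explanations for each outcome:

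- **Metabolic and renal outcomes (Hypothesis 5).** GH coaching draws on 17 possible behaviour changes, among them less sodium, more protein and lower cholesterol. Hypothesis 1 separately predicts that diet counselling changes food choices.
- **Well-being (Hypothesis 6).** Coaching sets out to move patients' feelings about their health from negative to positive. Frequent personal attention could also raise self-reported well-being.
- **Activity and inflammation (Hypotheses 3 and 4).** The programme includes cardio weeks, diet change and regular prompting between sessions.

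A positive between-arm result could therefore arise partly or wholly from components other than resistance exercise. If Hypotheses 3 to 6 are tested and reported as worded, that result would be published as an effect of strength training, or as macrophage activation by it. The design could not support that conclusion even if the trial were run without fault.

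**Working it through.** **1. What each arm receives**

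| Component | GH | Control | Section |
|---|---|---|---|
| Resistance exercise | yes | no | Summary of GH Study Visits |
| Cardio weeks | yes | no | weekly programme table |
| Coaching on diet and behaviour | yes | no | Coach Them to Make Sustainable Improvements |
| Cognitive, motivational and NLP techniques | yes | no | Change Feeling and Thinking Patterns |
| One-to-one sessions and follow-up contact | yes | no | Build and Expand Their Life Tissue; GH Study Visits |
| Standard nutrition evaluation and education | yes | yes | Counseling |

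Hypothesis 1 does not say which arm receives its twice-weekly diet counselling. Even if both arms did, the remaining components would still differ together.

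**2. Size of the bundle (scheduled, not delivered)**

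- Allocation: 180 + 45 = 225 and 180 / 45 = 4, as the plan states.
- First two weeks: 4 sessions × 75 min = 5 h.
- Remaining 50 weeks: 50 × 2 × 60 min = 100 h.
- Total: 105 h over 104 sessions. With every session at one hour, as Randomization words it, the total is 52 × 2 = 104 h.
- Follow-up contact: at least 2 × 52 = 104 attempts.
- Cardio weeks in the table: 6, 13, 18, 25, 41 and 52, so 6 of 52. That is about 6 × 2 = 12 h, leaving 105 − 12 = 93 h in the other 46 weeks.

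**3. What can be estimated**

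Write the difference in means between arms as

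Δ = strength + cardio + diet + psychological and behavioural coaching + attention + their interactions.

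The trial gives one equation, for Δ. As a check, take a design matrix of 225 rows with an intercept and one column for each of the five components: all ones for the 180 GH patients, and zeros after the intercept for the 45 controls. It has 6 columns and rank 2. Rank 2 means an intercept and one treatment contrast, so only Δ is estimable and no component can be separated.

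**4. Whether any planned analysis closes the gap**

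Statistical Analyses plans two-group t-tests and chi-square or Fisher tests, with no component, mediation or dose-response analysis. Activity and vascular function are not on the efficacy list, but any comparison of them would be between the same two arms. The optional biopsy does not help. It is a single sample without baseline, limited to certain fistula types, and its timing rule differs by arm.

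**5. Whether correlating changes would close it**

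Associating change in DEXA lean mass or Biodex strength with change in each marker would not separate strength training from diet, cardio or coaching, because every GH patient is assigned all of them. It would also add many tests. The plan names about 1 macrophage ratio + 8 pro-inflammatory + 2 pro-regenerative + 7 metabolic or renal markers = 18. With two predictors this is 36 tests, and 36 × 0.05 = 1.8 would be expected below 0.05 if nothing were associated. The plan has no multiplicity control.

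**The case against.** The strongest reply is that strength training is shorthand for allocation to GH. Hypothesis 3 ends by calling the arms control and GH. Hypothesis 6 goes straight on to counselling. Resistance work fills 46 of the 52 programme weeks. The title, the aim, the efficacy criteria and the two-group tests are all at programme level, and no planned analysis estimates a strength-only effect. Testing a package against usual care is a legitimate design.

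Most of this stands, and it limits the point to the wording of the hypotheses and the conclusions they permit. It does not remove the point. Hypothesis 2 shows that the authors can name the combination when they mean it, and the rationales in Hypotheses 3 to 5 are specific to strength or muscle, which goes beyond a label.

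Three stronger readings are tempting, and the documents support none of them:

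- **That the randomised comparison is invalid.** It answers the stated aim.
- **That the protocol already asserts a proven mechanism.** These are hypotheses, and the mechanisms in 4 and 5 are put tentatively.
- **That controls receive no nutrition or exercise input.** Both arms receive the standard nutrition evaluation and education, and Background says that the transplant team routinely recommends exercise.

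Hypotheses 3 and 6 also name a physical therapy comparator that is not randomised. Correcting only that would leave strength training as the credited cause, so both changes belong in one edit.

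**Conclusion.** The point holds as a mismatch between Hypotheses 3 to 6 and the randomised contrast. The effect of the GH programme against standard care is estimable. The part of it due to strength training, and any mechanism running through muscle mass or type II macrophages, is not identified by the between-arm comparison. No share can be given: the data would be compatible with strength training contributing none, some or all of the difference. That is a statement of non-identification, not an estimate of bias.

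The 105 hours describe the schedule. Weeks may be repeated or skipped, and trained personnel may run sessions from written instructions, so delivered content may differ. The conclusion does not depend on the hours. It needs only that the components are allocated together.

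This should be corrected before results are reported. It changes what the trial may conclude, and leaves conduct and testing as they are.

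**What to change.** - In Hypotheses 3 to 6, replace *strength training* with *the GH programme (exercise, nutrition and coaching)*. In the same edit, replace the physical therapy, no-treatment and other-group comparators with *standard-of-care control*.
- Add one sentence to Statistical Analyses: between-arm results support conclusions about the programme as a whole only.
- Label the muscle-mass and macrophage rationales as hypothesis-generating.
- Optional: an analysis of change in lean mass or strength against change in a few markers named in advance. Label it exploratory and non-randomised, and report it with a statement that it cannot separate strength training from diet, cardio or coaching.

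The cost is an edit to four hypotheses and one added sentence, with no new patients, visits or measurements. The downside is a narrower claim. Isolating strength training would take a further arm matched on diet, coaching and contact, which the stated aim does not require.
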